11.2. Statistical Methods

This section describes the planned statistical analyses in general terms. A complete description of the methodology will be specified in a statistical analysis plan (SAP), which will be finalized prior to unblinding. Any changes in the statistical methods described in this protocol that occur prior to unblinding will be documented in the statistical analysis plan and will not require a protocol amendment.

11.2.1. General

Statistical analyses will be performed using two-sided tests at alpha level of 0.05.

Data will be summarized by treatment group (and by visit when applicable), with respect to demographic and baseline characteristics, efficacy variables, and safety variables.

Summary statistics will include the mean, N, standard deviation, median, minimum, and maximum values for continuous variables, and frequencies and percentages for categorical variables.

For the analyses of change from baseline, only patients with a baseline and at least one post-baseline measure will be included in the analysis. Unless otherwise specified, baseline is defined as the latest non-missing observation across all the visits in the screening phase, before the active study drug begins. Endpoint will be the latest non-missing observation across all the post-baseline visits in the treatment phase.

Low enrolling sites will be pooled for analysis and the pooling algorithm will be determined prior to breaking the blind. The goal of pooling low enrolling sites is to have a sufficient number of patients per treatment group within a site for the analysis models. Unless otherwise specified, the pooled sites will only be used in the analyses where the site has an effect. The actual sites rather than the pooled sites will be specified in the data listings.

Details of the model and the analyses will be specified in the SAP. All statistical analyses will be performed using SAS®, Version 9.1.3 or higher.

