To evaluate the efficacy of iloperidone monotherapy compared to placebo in the treatment of adult patients with bipolar I disorder experiencing an acute manic or mixed episode as measured by reduction in the Young Mania Rating Scale (YMRS) total score at Week 4

Secondary Objective(s):

- To evaluate the efficacy of iloperidone monotherapy compared to placebo in the treatment of adult patients diagnosed with bipolar I disorder experiencing an acute manic or mixed episode as measured by improvements in the Clinical Global Impression of Severity (CGI-S)
- To evaluate the efficacy of iloperidone monotherapy compared to placebo in the treatment of adult patients diagnosed with bipolar I disorder experiencing an acute manic or mixed episode as measured by reduction in the Young Mania Rating Scale (YMRS) total score at each trial visit
- To assess the rate of YMRS responders. A YMRS responder is defined as at least a 50% decrease from baseline in YMRS total score
- To assess the efficacy of iloperidone monotherapy compared to placebo in improving clinical symptomatology in adult patients diagnosed with bipolar disorder, manic or mixed episodes after acute treatment as measured by CGI-C
- To assess the efficacy of iloperidone monotherapy compared to placebo in improving clinical symptomatology in adult patients diagnosed with bipolar disorder, manic or mixed episodes after acute treatment as measured by MADRS
- To assess the safety and tolerability of iloperidone compared to placebo in the treatment of adult patients in an acute manic or mixed episode of bipolar I disorder as measured by changes in vital signs and weight, laboratory analytes, electrocardiograms (ECGs), and the incidence and severity of TEAEs and extrapyramidal symptoms (EPS) using the Barnes Akathisia Scale, Simpson-Angus Scale, and the AIMS

Exploratory Objective:

• To conduct a whole genome association scan to identify potential markers of response and safety for a bipolar indication

Open-label Extension (OLE) Objective:

• To explore the long-term safety and tolerability of dosing with iloperidone over an additional 52 weeks of treatment

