Subjects who complete the Double-Blind Treatment Period will be eligible to participate in the optional OLE Phase. Eligible subjects will enter the 7-day OLE Titration Period where iloperidone will be titrated to 24 mg/day total daily dose given as a bid regimen (12 mg bid). The target dose for CYP2D6 poor metabolizers is 12mg/d (6 mg bid). Subjects will then enter the OLE Maintenance Period in which subjects will be treated with iloperidone for up to 52 weeks.

Criteria for evaluation:

Mean baseline-to-endpoint change in total score using following parameters:

Efficacy:

- Young Mania Rating Scale (YMRS)
- Overall and mania severity of illness for Clinical Global Impression of Severity (CGI-S)
- Clinical Global Impression of Change (CGI-C)
- Montgomery-Asberg Depression Rating Scale (MADRS)

Safety:

- Adverse Events (AEs) and proportion of patients withdrawing due to AEs
- EPS scale scores as measured by Simpson-Angus Scale (SAS), Abnormal Involuntary Movement Scale (AIMS), and Barnes Akathisia Rating Scale (BARS)
- Metabolic risk factors, clinical chemistry, hematology, vital signs, and weight
- Columbia Suicide-Severity Rating Scale (C-SSRS)
- CYP2D6 genotyping
- 12-lead electrocardiograms (ECG)

Statistical methods:

If not otherwise specified, statistical significance is defined as $p \le 0.05$ and is two-tailed when appropriate. Data base lock will occur after 4-week ST double-blind period. The primary efficacy variable is the change from baseline in the YMRS total score.

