11. STATISTICAL PLAN

11.1. Sample Size and Accrual

Based on a two-sided t-test with the 5% significant level, the planned sample size of 200 subjects per arm (a total of 400 subjects) provides around 90% power to detect a mean difference of 3.6 in YMRS (change from baseline at week 4) assuming a standard deviation of 11 in each treatment group.

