11.2.2. Patient Populations for Analysis

The following analysis populations will be defined for this study:

Intent-to-Treat: will include any patient randomized into the study that receives a dose of study drug and that has completed at least one post-baseline efficacy measurement while on study medication;

Safety: Any patient randomized into the study that receives a dose of study drug;

Per-Protocol: Any patient who is randomized and receives the protocol required study drug exposure and required protocol processing.

Efficacy analyses will be performed on the Intent-to-Treat population and the Per-Protocol population. Safety summaries will be based on Safety set. Patient characteristics will be presented for all patients randomized.

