11.3.2. Secondary Outcomes

The other secondary efficacy outcomes include:

- Responder
- CGI-S
- CGI-C
- MADRS

These outcomes will be analyzed similarly as the primary outcome. The categorical endpoints will be analyzed by a Cochran-Mantel-Haenszel test with adjusting for sites.

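### The protocol sets a default two-sided 0.05 for all analyses and states no gate, order or adjustment for the four secondary efficacy outcomes

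*Combined protocol and SAP*

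**What the plan says.** - **Significance level.** Section 11.2.1: "Statistical analyses will be performed using two-sided tests at alpha level of 0.05". The Synopsis, under statistical methods, gives a matching default: "If not otherwise specified, statistical significance is defined as" a p-value of 0.05 or less.
- **Primary.** Section 11.3.1 names one outcome at one time point, YMRS change at Week 4, analysed by MMRM.
- **Secondaries.** Section 11.3.2 opens with "The other secondary efficacy outcomes include" and lists responder, CGI-S, CGI-C and MADRS. They are analysed in the same way as the primary, with a Cochran-Mantel-Haenszel test for categorical endpoints. The section gives no rank, no condition on the primary and no adjustment, and it does not mention the SAP.
- **Objectives.** The Synopsis lists the secondary objectives in a different order (CGI-S, per-visit YMRS, responder, CGI-C, MADRS). It includes "reduction in the Young Mania Rating Scale (YMRS) total score at each trial visit", which 11.3.2 does not list. Its evaluation criteria give CGI-S two scores, overall and mania.
- **Populations.** Section 11.2.2: "Efficacy analyses will be performed on the Intent-to-Treat population and the Per-Protocol population". Neither is named as decisive.
- **Deferral.** Section 11.2 calls its own content general and leaves the complete methodology to a SAP to be finalised before unblinding. Changes made before then need no protocol amendment.

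**The concern.** The protocol gives a significance rule and does not limit it to the primary. Read literally, any of the four secondaries with p at or below 0.05 is significant, whatever the primary shows and whatever the other three show. The CGI-S, CGI-C and MADRS objectives are worded as efficacy against placebo. Only the genome scan is labelled exploratory, so a reader of the trial report has no stated reason to treat a nominally significant secondary as descriptive.

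What is at stake is the credibility of secondary findings. With four chances at 0.05, an isolated positive is weaker evidence than its p-value suggests. An order chosen after unblinding would not repair that.

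**Working it through.** **1. Reproduce the plan's own figure.** Section 11.1 says "the planned sample size of 200 subjects per arm (a total of 400 subjects) provides around 90% power" for a difference of 3.6, "assuming a standard deviation of 11 in each treatment group", with a two-sided 5% t-test.

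- Standard error = 11 × √(2/200) = 1.10
- 3.6 / 1.10 = 3.27
- Power = Φ(3.27 − 1.96) = 0.905 by the normal approximation, and 0.904 by the noncentral t with 398 degrees of freedom
- 90% power needs 197 per arm

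The stated figure holds. It concerns one comparison at 0.05, and the points below leave it unchanged.

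**2. Four secondaries at 0.05, independent, no effect on any.**

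1 − (1 − 0.05)^4 = 1 − 0.8145 = 0.1855, which is 0.1855 / 0.05 = 3.7 times nominal.

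For jointly normal test statistics and two-sided tests, independence is the worst case (Šidák's inequality), so 18.5% is a ceiling under that model.

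**3. Allow for correlation.** The four outcomes are measured in the same patients, so the test statistics will be correlated. The documents give no correlations, so the values of ρ below are assumptions. With a common correlation ρ and c = 1.96:

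P(at least one) = 1 − ∫ φ(u) [Φ((c − √ρ u)/√(1−ρ)) − Φ((−c − √ρ u)/√(1−ρ))]^4 du

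The last column drops the lower-tail term, so it counts only false findings in favour of iloperidone, with nominal 2.5%.

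| Assumed ρ | At least one false positive | Multiple of 5% | In favour of iloperidone |
|---|---|---|---|
| 0 | 18.5% | 3.7 | 9.6% |
| 0.3 | 17.4% | 3.5 | 8.7% |
| 0.5 | 15.6% | 3.1 | 7.8% |
| 0.7 | 13.0% | 2.6 | 6.5% |
| 0.8 | 11.4% | 2.3 | 5.7% |
| 0.9 | 9.4% | 1.9 | 4.7% |

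Simulation with 1,000,000 draws agrees with these values to within 0.1 percentage point.

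**4. If both CGI-S scores are tested.** Five tests give 1 − 0.95^5 = 22.6% if independent, 18.3% at ρ = 0.5 and 12.7% at ρ = 0.8. The count of tests therefore depends on a choice that the plan has not made.

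**5. Compare with a controlled procedure.** In a fixed sequence gated on the primary, each test is reached only after every earlier one is significant at 0.05. A false positive requires rejecting the first true null hypothesis in the sequence, which has probability at most 0.05 at any correlation. For comparison, Bonferroni over four tests (0.05/4 = 0.0125 each) gives 1 − 0.9875^4 = 4.9% if independent and 3.2% at ρ = 0.8.

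**The case against.** **The SAP may settle this.** Section 11.2 is a general description, 11.2.1 sends details of the models and analyses to the SAP, and the Synopsis rule is only a default. A hierarchy in the SAP would answer the point, and this stands as a limit on it: the protocol cannot be said to have adopted a wrong final rule. But the items specifically deferred are the primary model and supportive analyses (11.3.1), adverse-event incidence (11.4.1.1), laboratory incidence (11.4.1.2), EPS (11.4.1.5), C-SSRS (11.4.1.6) and subgroups (11.5). Multiplicity is not named, and a significance default is in force until something replaces it.

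**No secondary is called key or confirmatory.** This is true, and no section says that a positive secondary supports a claim when the primary fails. Labelling the secondaries descriptive would also resolve the point. The text does not do so.

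**A reader might infer that every visit and both populations are formal tests at 0.05**, and so quote a larger inflation. The documents do not support that. Per-visit YMRS is a Synopsis objective but is absent from 11.3.2, and 11.2.1 mentions visits only for summaries. Section 11.2.2 runs efficacy analyses on two sets without saying that a Per-Protocol result can stand alone. The material reviewed does not give the number of visits, so any figure for that wider family rests on assumptions.

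**A reader might also infer that the primary is compromised.** It is not: one outcome at one time point is tested, and secondary tests do not alter its error rate.

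**Conclusion.** The point holds for the four outcomes in 11.3.2. The text reviewed has a default significance level and no multiplicity rule for them. If the default is followed, the inflation is about 2 to 3.7 times nominal.

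This rests on three assumptions: no effect on any of the four, one test per outcome on one population, and correlations chosen for illustration. The error stays above 5% throughout the range examined. A single multiple such as three to four times should not be quoted as fact, because it falls to 2.3 at a correlation of 0.8.

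This is worth correcting before unblinding. It does not threaten the primary conclusion.

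**What to change.** Add a short paragraph to 11.3.2 or to the SAP before unblinding. Section 11.2 allows the SAP route without a protocol amendment. It should state that:

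1. Secondaries are tested only if the Week 4 YMRS primary is significant at two-sided 0.05 on the Intent-to-Treat set.
2. They are then tested on that set in one pre-specified fixed order, each at two-sided 0.05, stopping at the first non-significant result.
3. The sponsor sets the order. The Synopsis and 11.3.2 list the outcomes differently and neither list is a ranking, so neither can be adopted by default.
4. The CGI-S entry names which score is tested, overall or mania.
5. Per-visit YMRS, Per-Protocol results and any secondary outside the sequence carry nominal p-values with no claim of significance.

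If no secondary claims are intended, one sentence making all secondary p-values nominal is enough. If the SAP already contains such a rule, a cross-reference from 11.3.2 suffices.

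**Cost.** The change takes no alpha from the primary and adds no patients. The downside is that once one secondary fails, those after it cannot be claimed however small their p-values, so the order needs thought.

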11.2.2. Patient Populations for Analysis

The following analysis populations will be defined for this study:

Intent-to-Treat: will include any patient randomized into the study that receives a dose of study drug and that has completed at least one post-baseline efficacy measurement while on study medication;

Safety: Any patient randomized into the study that receives a dose of study drug;

Per-Protocol: Any patient who is randomized and receives the protocol required study drug exposure and required protocol processing.

Efficacy analyses will be performed on the Intent-to-Treat population and the Per-Protocol population. Safety summaries will be based on Safety set. Patient characteristics will be presented for all patients randomized.

11.2.3. Patient Disposition

Study completion and reasons for discontinuation for all randomized patients in the treatment phase will be summarized for each treatment group. Discontinuations by reason will be tabulated for each treatment group.

As needed, time to discontinuation due to adverse events, lack of efficacy and for any reason may be analyzed using Kaplan-Meier survival techniques; the log-rank test may be used for group comparison.

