1. SYNOPSIS

Name of Sponsor/Company: Vanda Pharmaceuticals Inc.

Name of Investigational Product: iloperidone

Name of Active Ingredient: iloperidone, VYV-683

Title of Study: A multicenter, randomized, double-blind, placebo-controlled study to evaluate the efficacy and safety of iloperidone for 4 weeks in the treatment of patients with acute manic episodes associated with Bipolar I Disorder

Study center(s): Approximately 50 sites across the U.S. and Europe

Studied period (years):

Phase of development:

Estimated date first patient enrolled: March 2021

Phase III

Estimated date last patient completed (through the Short-Term

Treatment Phase): May 2022

Number of patients (planned): 400 (200 iloperidone and 200 placebo)

Diagnosis and main criteria for inclusion:

- Meet the *Diagnostic and Statistical Manual of Mental Disorder, Fifth Edition* (DSM-5) diagnosis of bipolar I disorder, manic or mixed type, as confirmed by the Structured Clinical Interview for Diagnostic and Statistical Manual of Mental Disorders, Fifth Edition (SCID) manic or mixed type with or without psychotic symptoms
- Men and women between the ages of 18-65 years inclusive
- Had at least one prior documented manic or mixed episode (with or without psychotic symptoms) that required treatment prior to screening
- Patients with Young Mania Rating Scale (YMRS) total score ≥ 20
- Patients with ≥ 4 on at least 2 of 4 YMRS items (irritability, speech, content, disruptive/aggressive behavior)
- Patients with Montgomery-Asberg Depression Rating Scale (MADRS) total score < 18
- Voluntarily hospitalized for current manic episode

Main Exclusion Criteria:

- Patients with a DSM-5 diagnosis other than bipolar I disorder that was the primary focus of treatment within the previous six months
- Patients experiencing a first manic episode or meeting criteria for rapid cycling

Investigational product, dosage and mode of administration:

Iloperidone will be provided as overencapsulated tablets containing either 1, 3, 6, 9, or 12 mg.

Duration of treatment:

Short Term Double-Blind Treatment Phase (4 weeks)

Titration Period – 1 week

Double-Blind Treatment Period – 3 weeks

Optional Open-Label Extension Phase (52 weeks)

Open-label Titration Period – 1 week

Open-label Extension Period – 51 weeks

Reference therapy, dosage and mode of administration:

Placebo will be provided in size and appearance that are visually identical to those containing iloperidone.

Primary Objective:

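### Kaplan-Meier curves for discontinuation due to AEs or lack of efficacy, if other-reason dropouts are censored, would overstate the proportion stopping for that cause and not match the by-reason table

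*Combined protocol and SAP*

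**What the plan says.** Section 11.2.3 makes one firm commitment and one optional one.

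- **Firm:** "Study completion and reasons for discontinuation for all randomized patients in the treatment phase will be summarized for each treatment group", and "Discontinuations by reason will be tabulated for each treatment group". These are crude proportions by arm among all randomized patients.
- **Optional:** as needed, "time to discontinuation due to adverse events, lack of efficacy and for any reason may be analyzed using Kaplan-Meier survival techniques", and "the log-rank test may be used for group comparison". One method is named for three endpoints. The section states no censoring rule and no competing-risk method.

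Section 11.2 adds that "A complete description of the methodology will be specified in a statistical analysis plan (SAP), which will be finalized prior to unblinding". The reviewed text contains no separate SAP section on disposition, so the method named in Section 11.2.3 is the only one on record.

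Withdrawal due to AEs also appears as a proportion in the safety criteria of the Synopsis and in Section 11.4.1.1.

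**The concern.** Kaplan-Meier suits discontinuation for any reason, because no other way of leaving treatment competes with it. For a single cause the usual practice is to censor a patient on leaving for another reason. The estimator then removes that patient from the risk set and credits them with the same future chance of stopping for the cause as those who remain. But that patient can no longer stop for it. So 1-KM describes a hypothetical setting without the other reasons, and even that only if the reasons are independent. It is not the proportion who stop for the cause.

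A report could then carry two figures for what most readers would take as the same quantity: a week-4 curve value and a lower table entry. The cause-specific curves would also add up to more than the any-reason curve. If dropout for other reasons differs between arms, the gap between curve and table differs too, and a difference read off the curves would differ from the one in the table.

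**Working it through.** **Inputs from the documents.** 200 patients per arm and a 4-week (28-day) double-blind phase (Synopsis). No dropout rate is given, whether overall, by cause or by arm, so every rate below is an assumption.

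**The plan's own figure.** The disposition analysis has none. The only reproducible figure nearby is the power in Section 11.1: 3.6 / (11 × √(2/200)) = 3.6 / 1.1 = 3.273, and Φ(3.273 − 1.960) = 0.905 (0.904 with the noncentral t), against the stated value of around 90%. It reproduces, and this point does not depend on it.

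**Direction.** Cumulative incidence weights each increment of the cause-specific hazard by the probability of still being on treatment at all. 1-KM weights it by the larger probability of not yet having stopped for that cause. So 1-KM cannot be lower, and it is higher once some other-reason dropouts precede dropouts for the cause. This needs no constant-hazard assumption.

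**Size.** Assume constant hazards. Let c be the true week-4 proportion stopping for the cause, o the proportion stopping for all other reasons, and T = c + o. The total cumulative hazard is −ln(1 − T), of which the cause takes the share c/T. Hence

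1-KM = 1 − (1 − T)^(c/T).

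| c | o | T | cause hazard over 28 days | 1-KM | 1-KM / c |
|---|---|---|---|---|---|
| 6% | 20% | 26% | 0.0695 | 6.7% | 1.12 |
| 6% | 30% | 36% | 0.0744 | 7.2% | 1.19 |
| 6% | 40% | 46% | 0.0804 | 7.7% | 1.29 |

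Across a wider grid (c from 2% to 15%, o from 5% to 40%) the excess runs from 0.05 points (2% and 5%) to 4.6 points (15% and 40%).

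**Any reason.** With o = 0 the formula returns c: 30% stays 30%.

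**Adding up.** With AE, lack of efficacy and other at 10%, 5% and 10%, the three 1-KM values are 10.87%, 5.59% and 10.87%. They sum to 27.3% against a true 25%.

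**Between arms.** Rates are AE / lack of efficacy / other. Differences are iloperidone minus placebo, in points, shown as true → 1-KM.

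| Iloperidone | Placebo | AE difference | Lack-of-efficacy difference |
|---|---|---|---|
| 8/8/14% | 8/8/14% | 0 → 0 | 0 → 0 |
| 9/6/15% | 5/12/15% | 4.0 → 4.3 | −6.0 → −6.6 |
| 10/5/10% | 5/15/20% | 5.0 → 4.7 | −10.0 → −11.8 |

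In the first row each arm is overstated by 1.07 points for each cause, and the difference is unbiased. In the other rows the AE difference moves by 0.3 points, up in one and down in the other.

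**Log-rank test.** In 10,000 simulated trials of 200 per arm, with equal AE hazards (0.10 over 28 days) and competing hazards of 0.15 and 0.50, the two-sided 5% test rejected in 4.9% (Monte Carlo standard error 0.2 points). It keeps its size as a test of cause-specific hazards. In that setting 1-KM is 1 − exp(−0.10) = 9.5% in both arms. Cumulative incidence is (0.10/0.25)(1 − exp(−0.25)) = 8.8% in one and (0.10/0.60)(1 − exp(−0.60)) = 7.5% in the other.

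**The case against.** The strongest reply is that the plan already reports the right quantity. The by-reason table in Section 11.2.3 and the AE-discontinuation proportions in Section 11.4.1.1 give crude week-4 figures, and the safety criterion in the Synopsis is itself a proportion. The curves are optional, Section 11.2.3 never says they will be read as absolute risks, and detail is deferred to a SAP. All of that stands, and it limits the consequence. It does not remove the point: Kaplan-Meier is the method named for the two causes, and nothing in the reviewed text replaces it.

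A second reply is that the two methods answer different questions. With 6% AE discontinuation in both arms but other-cause dropout of 20% and 40%, the curves read 6.7% and 7.7%. That one-point gap is not pure artefact. The AE hazards are 0.0695 and 0.0804, a ratio of 1.16, so AE discontinuation really is faster among those still on treatment in the second arm. Conversely, equal hazards give unequal cumulative incidence, as in the simulated setting. This also stands. Cumulative incidence is preferable here because the plan's other summaries of the same event are proportions. The gap is also small: with 200 per arm its standard error is √[(0.067 × 0.933 + 0.077 × 0.923)/200] ≈ 2.6 points.

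A reader might infer three stronger things:

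- **That the overstatement is unequal between arms.** The documents give no dropout rates, and identical patterns give equal overstatement.
- **That the log-rank comparison is invalid.** It is a valid test of cause-specific hazards.
- **That the plan specifies the censoring.** It does not; the rule is inferred from usual practice.

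**Conclusion.** The point holds as a minor one. If the optional AE and lack-of-efficacy curves are produced by Kaplan-Meier with other-reason dropouts censored, and are read as proportions, they are too high and will disagree with the by-reason table. Under assumed other-cause dropout of 20% to 40% and constant hazards, the excess on a true 6% is 0.7 to 1.7 points, or 12% to 29% in relative terms. Whether it differs between arms depends on dropout patterns that the documents do not give.

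The any-reason curve is unaffected. The tabulated proportions remain correct, provided that each patient's completion or reason for stopping is recorded. The primary analysis, power and sample size are not touched.

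**What to change.** In the disposition section of the SAP:

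1. Keep Kaplan-Meier, with the log-rank test if wanted, for discontinuation for any reason.
2. For discontinuation due to AEs and due to lack of efficacy, present Aalen-Johansen cumulative incidence curves by arm, with all other reasons as competing events. With complete follow-up to week 4 these end at the tabulated proportions, and with every reason shown they add up to the any-reason curve.
3. Label any log-rank test on these two causes as a comparison of cause-specific hazards, and state that other-reason dropouts are censored for that test.

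The cost is a small programming change and one extra method to describe for an optional output. Section 11.2 lets the SAP record changes of method before unblinding without a protocol amendment.
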